4.2.1 PRIMARY ENDPOINT

- 1) Intradialytic hypotension: measured on a per-treatment basis; defined as nadir systolic BP <90 mmHg
- 2) Troponin T change: measured at the 7th treatment of each phase; defined as pre-HD – post-HD troponin T (ng/mL) and percentage change (troponin T rise) $\geq 10\%$
- 3) Left ventricular global longitudinal strain (GLS) on TTE: measured at baseline and 30 minutes before HD end during 7th treatment in the first phase of each treatment type (once during conventional and once during UF profiled treatment); defined as % GLS change (intradialytic GLS – baseline GLS), see Appendix A for TTE protocol. A change $\geq 2.5\%$ indicates a clinically important change in GLS.

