4.2.3 EXPLORATORY ENDPOINTS

1) Early diastolic myocardial velocity (Em): measured 30 minutes before HD end during 7th treatment in the first phase of each treatment type (once during conventional and once during UF profiled treatment); calculated as the average of early diastolic velocities recorded at the medial and lateral mitral annulus, see Appendix A for TTE protocol

2) Tricuspid annulus systolic excursion velocity (S_t): measured 30 minutes before HD end during 7th treatment in the first phase of each treatment type (once during conventional and once during UF profiled treatment); measured as the distance of tricuspid annular movement between end-diastole to end-systole (cm), see Appendix A for TTE protocol

3) Blood volume monitor slope (by hour): measured during the 1st (last) HD treatment of each week, hour-by-hour basis; defined as change in blood volume (%) on an hourly basis

4) Blood volume monitor slope (by treatment): measured during the 1st (last) HD treatment of each week, from start to end of HD treatment; defined as change in blood volume (%) over the entire HD treatment

5) Plasma refill: measured 10 minutes before HD end during 7th treatment of each phase; defined as the percentage increase in hematocrit

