7.2.2 OTHER ASSAYS OR PROCEDURES

TTE: Patients will undergo intradialytic TTE at baseline (within 6 weeks prior to study start) and 30 minutes prior to HD end ("peak stress") during treatment 7 of the first phase of each treatment type (once during conventional and once during UF profiled treatment) (1 TTE during UF profiled HD and 1 during control HD). Study TTEs will be performed by a trained sonographer with a Philips CX50 ultrasound system (Philips North America).

Blood volume monitoring: Blood volume monitoring will be performed continuously throughout each study treatment via a Crit-line™ (standard-of-care non-invasive relative blood volume monitoring tool used as part of standard dialysis treatments).

Plasma refill test: Using the blood volume monitor, a plasma refill test will be performed 10 minutes before HD end during the 7th treatment of each phase. At the start of the treatment, UF time will be set 10 minutes less than treatment time. When the dialysis UF ends, study staff will document the hematocrit (%) from the blood volume monitor, and when the treatment ends, document the blood volume monitor hematocrit (%) again. Plasma refill tests are part of the blood volume monitoring protocols at the selected units and are familiar to staff.

Patient acceptance: At the end of the 9th study treatment of each phase, study staff will ask the participant the following question: "If recommended by your physician, would you be willing to adopt the HD prescription you have received during the last 9 treatments?"

Symptom assessment: At the conclusion of the 1st study treatment each week, study staff will ask patients to complete a symptom questionnaire (Appendix B).

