10.2 STATISTICAL HYPOTHESES

We hypothesize that patients will have comparatively less hypotension, troponin change and left ventricular global longitudinal strain change with UF profiling vs. conventional HD.

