10.4.2 ANALYSIS OF THE PRIMARY EFFICACY ENDPOINT(S)

Comparisons of values for the binary primary endpoints of hypotension and troponin T rise $\geq 10\%$ between HD treatments will be performed using generalized estimating equations. Comparisons of values for the continuous

primary endpoint of global longitudinal strain change will be performed using ANOVA or non-parametric methods depending on data type.

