10.5 SAMPLE SIZE

This cross-over study is designed as a pilot study to test for efficacy signals. However, with its cross-over design in which each participant acts as his or her own control, we are powered to detect clinically and statistically significant differences across arms within patients. With a sample size of 30, we have 80% power to detect a 5.9 mmHg difference in nadir SBP (S.D. 8), a ≥ 0.07 ng/mL troponin T difference (S.D. 0.1), a 2.2% strain difference (S.D. 3), and 4% ejection fraction difference (S.D. 5); all clinically meaningful differences. We have 80% power to detect a 31% absolute difference in the binary endpoint of Troponin T change >0.1 ng/mL (event rate=20%).

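### Plasma refill is scored backwards: section 4.2.3 counts an increase in hematocrit, but refill in the section 7.2.2 test lowers it (low severity). The continuous troponin T difference also runs against the rise named beside it.

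*Combined protocol and SAP*

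**What the plan says.** **Plasma refill.** Section 4.2.3 lists it last of five exploratory endpoints: "Plasma refill: measured 10 minutes before HD end during 7th treatment of each phase; defined as the percentage increase in hematocrit". Section 7.2.2 describes the test. At the start of treatment, "UF time will be set 10 minutes less than treatment time". Then: "When the dialysis UF ends, study staff will document the hematocrit (%) from the blood volume monitor, and when the treatment ends", the monitor's hematocrit is recorded a second time. Section 10.4.11 assigns the endpoint to ANOVA or a non-parametric method. The SAP, under Continuous Outcomes, uses a linear model with a random intercept and log-transforms outcomes that are percentages. It does not list endpoints or repeat any endpoint formula.

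**Troponin T.** Section 4.2.1 has two components in one line, "defined as pre-HD – post-HD troponin T (ng/mL) and percentage change (troponin T rise" of at least 10%). Section 10.4.2 names the "binary primary endpoints of hypotension and troponin T rise" of at least 10%. Section 10.5 powers a "binary endpoint of Troponin T change >0.1 ng/mL (event rate=20"%). Section 10.2 expects "comparatively less hypotension, troponin change and left ventricular global longitudinal strain change" with UF profiling.

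No section states a sign convention for either variable.

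**The concern.** An endpoint called plasma refill should be larger when there is more refill. In this test UF is off between the readings, so fluid entering the vessels dilutes the red cells and hematocrit falls. Coded as written, refill comes out negative, and the session with more refill gets the lower number. A reader of the results table who takes a higher score as more refill would read the treatment difference the wrong way round. Section 10.4.1 says that the size of estimates and their confidence intervals will be weighed in interpretation, so direction has to be clear.

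There is also a practical problem. If the SAP's rule for percentage outcomes is applied to this endpoint, the analysis fails for every session in which refill occurs.

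The troponin T difference raises a lesser question of the same kind. Earlier minus later is natural for a quantity expected to fall, as with systolic BP and ejection fraction in section 4.2.2. It is awkward for a marker whose event is a rise.

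**Working it through.** The plan gives no figure for refill and none that depends on a sign, so the check is on direction.

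**1. Refill.** Inputs: the two reading times and the UF-off interval (section 7.2.2) and the definition (section 4.2.3). Assumptions, not in the documents: red-cell volume is constant over the 10 minutes; starting hematocrit is 36%; blood volume grows by a fraction r.

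Hct2 = Hct1 / (1 + r)

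As defined: 100 x (Hct2 - Hct1) / Hct1. Reversed: 100 x (Hct1 - Hct2) / Hct1. Log ratio: 100 x ln(Hct1 / Hct2) = 100 x ln(1 + r).

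| r | Hct2 (%) | As defined | Reversed | Log ratio |
|---|---|---|---|---|
| 0 | 36.00 | 0 | 0 | 0 |
| 1% | 35.64 | -0.99% | +0.99% | 1.00 |
| 2% | 35.29 | -1.96% | +1.96% | 1.98 |
| 3% | 34.95 | -2.91% | +2.91% | 2.96 |
| 5% | 34.29 | -4.76% | +4.76% | 4.88 |

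The starting value of 36% cancels from all three scores. The score as defined is negative whenever r > 0 and falls as r grows.

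**2. The log transform.** log(-1.96) is undefined, as is the log of every other negative entry. Reversing the sign cures this where r > 0. A session with no measurable refill still scores 0, and one in which the second reading is higher still scores below 0. The log ratio exists for any two positive readings.

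**3. Troponin T.** Illustration: 0.100 ng/mL before and 0.112 ng/mL after.

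- Difference as written: 0.100 - 0.112 = -0.012 ng/mL.
- Rise: 100 x (0.112 - 0.100) / 0.100 = +12%, which meets the 10% criterion.

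The two components in one line therefore carry opposite signs for the same session. The dash might be read as the word to, but in the strain, systolic BP, weight and ejection fraction definitions the same mark is a subtraction. The strain entry just below uses later minus earlier.

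**4. Does the sign affect inference?** Replacing y by -y in the SAP's linear model reverses the treatment coefficient and leaves its standard error unchanged. A simulated data set of 30 participants with four periods gave coefficients of -0.0386 and +0.0386, both with p = 0.031. (The fit warned of a variance near its boundary; the algebra does not depend on that.)

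For power, section 10.5 states 0.07 ng/mL with SD 0.1 and 30 participants. The two-group formula 0.1 x (1.960 + 0.842) x sqrt(2/30) = 0.072 rounds to that figure. Power at exactly 0.07 is 0.774 for either sign.

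**The case against.** The case for leaving the text alone has real force.

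- **Refill is exploratory and recoverable.** Both raw hematocrits are recorded, and section 7.2.2 says the staff know the test. That stands, and it keeps the severity low. It does not make the definition correct, and no other section corrects it.
- **The troponin order is a convention.** Earlier minus later is used elsewhere in the endpoint list, and a negative value for a rise is not in itself an error. That stands too: the fault is the unexplained clash with the word rise and with the positive threshold in section 10.5.

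Three stronger readings are tempting, and the documents do not support them.

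- *A reader might infer that the primary troponin endpoint would count falls as events.* Section 4.2.1 attaches the 10% threshold to the rise, not to the pre-minus-post difference, and section 10.4.2 analyses the rise. The 0.1 ng/mL threshold appears only in the sample-size text, and its mismatch with 10% is a separate matter.
- *A reader might infer that a benefit of profiling on the trial's mechanism would be reported as harm.* Section 2.2 does rest the rationale on UF outpacing refill. But no section calls this endpoint the test of that mechanism, section 10.2 gives no hypothesis for it, and nothing says that a larger fall in hematocrit is better or expected with profiling. Profiling lowers the UF rate late in treatment, which could itself alter the last 10 minutes.
- *A reader might infer that the tests or the power are invalid.* Section 10.4.1 makes all tests two-sided, and step 4 of the working shows no effect on untransformed outcomes.

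**Conclusion.** The plasma refill definition is wrong as written, at low severity. It scores the named quantity backwards, and under the SAP's log rule it cannot be computed when refill occurs. This rests on one step that the documents do not state: dilution at fixed red-cell volume over 10 minutes. The sizes shown are illustrations; the direction does not depend on them. The log problem further assumes that the SAP's rule covers this exploratory endpoint. The SAP speaks of endpoints generally and exempts none, while section 10.4.11 mentions no transform.

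The troponin point is secondary. The continuous difference should run in the same direction as the rise. The binary primary endpoint is already readable and is not affected. For untransformed outcomes, what is at stake in both variables is the direction of the reported estimate and nothing else.

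**What to change.** **Section 4.2.3:** define plasma refill as 100 x (Hct at UF end - Hct at treatment end) / Hct at UF end, and state that larger values mean more refill.

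**SAP, Continuous Outcomes:** exempt this signed percentage from the log transform, or analyse ln(Hct at UF end / Hct at treatment end) in its place. Reversing the sign alone is not enough, because zero and negative values can still occur.

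**Section 4.2.1:** define troponin T change as post-HD minus pre-HD (ng/mL), and the rise as 100 x (post - pre) / pre of at least 10%. Section 10.5 can then refer to the same signed change.

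**Cost:** two definitions in the protocol and one line in the SAP, plus the IRB review that section 13.2 requires for any amendment. Data collection does not change, since both hematocrits and both troponin T values are already recorded.

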5 STUDY ENROLLMENT AND WITHDRAWAL

5.1 PARTICIPANT INCLUSION CRITERIA

- UF rate >10 mL/h/kg in >30% of treatments in a 4-week screening period (require ≥6 outpatient treatments in this period)
- Age 18-85 years
- Ability to converse comfortably in English or Spanish
- Receipt of in-center maintenance HD at Carolina Dialysis Carrboro, Siler City, Pittsboro, Mebane, or Sanford clinics
- ≥90 days on HD
- Free of bloodstream infection during 4-week screening period
- Willingness to undergo all study testing
- Evidence of a signed and dated informed consent document

5.2 PARTICIPANT EXCLUSION CRITERIA

Patients meeting any of the following exclusion criteria will not be eligible for randomization.

- Systolic BP unable to be measured by arm cuff
- >1 hospitalization during 4-week screening period
- Unstable angina per treating nephrologist

- End-stage cirrhosis per treating nephrologist
- New York Heart Association class IV heart failure per treating nephrologist
- Pregnant
- Dialysis treatment schedule increases to more than 4 times per week
- Incarcerated
- Anticipated kidney transplant within 6 months per treating nephrologist
- Non-adherence to HD prescription (>2 unexplained absences during 4-week screening period)
- Sodium profiling or UF profiling in standing HD prescription
- Decisionally challenged, unable to provide informed consent

5.3 STRATEGIES FOR RECRUITMENT AND RETENTION

The recruitment goal is 36 participants (to account for drop-out) with study completion goal of 30 participants. The PI, a nephrologist, will identify eligible subjects from participating dialysis clinic (Carolina Dialysis Carrboro, Siler City) patient rosters and offer opportunity to participate in the study. If the patient does desire to participate in the research study, informed consent will be obtained by the PI or research staff. A study information sheet will be made available in the clinic for patients who desire additional information about the study. Participants will receive \$20 for their time spent participating in the baseline TTE procedure because it is the only TTE performed outside of participants' regular dialysis treatment time. Participants will be compensated \$45 for each 9 week treatment period and \$20 for the baseline period TTE (\$200 for full study completion).

Participants may miss study treatments. Missed study treatments will be considered "missed" and will not be made-up. For example, if a patient misses treatment #9 from arm 1, the patient will start wash-out treatments at the next treatment and will have missing data for treatment #9. The permeated design of the study arms (alternating conventional, UF profile, conventional, UF profile) was selected to maximize opportunities for data collection under each treatment paradigm. If participants are lost to follow-up (death, withdrawn consent, move to a new dialysis center), additional participants will be recruited until a study size of 30 participants is reached.

Based on the composition of the patient populations at the participating UNC sites, the expected sex breakdown is 50% male and 50% female and the expected enrollment of Hispanic or Latino participants is 10%. No exclusion by sex or by ethnic/ racial background will be made. There are no expected differences in the response to UF profiling across sex or racial/ ethnic groups. Children (individuals < 18 years) and vulnerable participants are not included in the study.

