4 STUDY DESIGN AND ENDPOINTS

4.1 DESCRIPTION OF THE STUDY DESIGN

The study is a 4-period cross-over trial (see schematic of study design) in which participants are successively alternated between study arms across 4 periods with intervening washout periods, and treatment order is randomized. The study control arm is conventional HD: the patient's standard HD prescription (no UF profiling). The study experimental arm is conventional HD + linear UF profiling. Linear UF profiling will be specified as a linearly decreasing UF rate with a UF rate starting at 1.33 times the rate that would be needed at a constant UF rate to achieve the desired post-weight (Fresenius 2008K machine profile 2). After providing consent, patients will be randomly allocated to experimental or control treatment for period 1. Patients will undergo 9 treatments during each phase for a total of 18 conventional HD treatments and 18 UF profiled treatments. Patients will undergo 3 wash-out HD treatments between phases. The study will be double-blinded in that patients will not be informed of the treatment paradigm. Investigators, including those performing TTE interpretation, will be blinded to treatment paradigm. Ultrasonographers performing intra-HD TTEs will be blinded to treatment paradigm.

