10.6 MEASURES TO MINIMIZE BIAS

10.6.1 ENROLLMENT/ RANDOMIZATION/ MASKING PROCEDURES

Randomization assignments will be generated using computer-generated random numbers. Assignments will be sealed in envelopes prior to study start. After patients consent to study participation, sealed study arm assignments will be randomly allocated to experimental or control treatment for period 1. Sequence assignments will be sealed in envelopes prior to study start and opened in a predetermined order at the start of each study period. The study will be double-blinded in that patients will not be informed of the treatment paradigm. Investigators, including those performing TTE interpretation, will be blinded to treatment paradigm. Ultrasonographers performing intra-HD TTEs will be blinded to treatment paradigm.

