Depending on the type of various endpoints, we propose to perform the following tests to test the difference between UF profile and conventional treatment.

- **Binary Outcomes**
 - We will perform repeated measure logistic regression by regressing the binary outcome on the treatment indicator and test if the coefficient before the treatment indicator is significant. Each subject will have a random intercept. The model is given by
$$\text{logit}(\text{outcome}) \sim 1 + \text{treatment} + (1|ID)$$
- **Continuous Outcomes**
 - We will perform repeated measure linear regression by regressing the continuous outcome (percentage outcome will be log-transformed) on the treatment indicator and test if the coefficient before the treatment indicator is significant. Each subject will have a random intercept. The model is given by
$$\text{outcome} \sim 1 + \text{treatment} + (1|ID)$$
- **Categorical Outcomes**
 - We will perform repeated measure multinomial regression by regressing the categorical outcome on the treatment indicator and test if the coefficient before the treatment indicator is significant. Each subject will have a random intercept. The model is given by
$$\text{multi-logit}(\text{outcome}) \sim 1 + \text{treatment} + (1|ID)$$

Quality Check

For patients who dropped out during the study, normalize endpoints to the same scale as the other patients, depending on the type of endpoints.

Sensitivity Analyses

1. Exclude participants who dropped out from all analyses.
2. Exclude participants who had endpoint data drawn "off-schedule" (troponin T, symptoms, etc.) from individual endpoint analyses.
3. Exclude participants who had an abnormality with their troponin T blood draw from troponin T-related analyses.
4. Test for difference by order of randomization (UF profiling --> conventional --> UF profiling --> conventional) vs. (conventional --> UF profiling --> conventional --> UF profiling)
5. Test for difference by clinic (site 1 vs. site 2)

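### With two alternating sequences the treatments lie four weeks apart within every completer, yet no SAP model has a phase term and no blocking of sequences is stated

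*Combined protocol and SAP*

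**What the plan says.** Protocol 4.1 states that "participants are successively alternated between study arms across 4 periods with intervening washout periods, and treatment order is randomized". Section 5.3 gives the reason for alternating: "alternating conventional, UF profile, conventional, UF profile) was selected to maximize opportunities for data collection under each treatment paradigm". Time trends are not mentioned there. The SAP (Sensitivity Analyses, item 4) names the two orders as "UF profiling --> conventional --> UF profiling --> conventional) vs. (conventional --> UF profiling --> conventional --> UF profiling".

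On timing, 4.1 says "Patients will undergo 9 treatments during each phase for a total of 18 conventional HD treatments and 18 UF profiled treatments" and "Patients will undergo 3 wash-out HD treatments between phases". Section 7.1.1 sets treatments at three per week.

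On allocation, 10.6.1 says "Randomization assignments will be generated using computer-generated random numbers". No ratio, blocking or stratification is given.

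On analysis, the SAP (Primary Analysis) fits continuous endpoints "by regressing the continuous outcome (percentage outcome will be log-transformed) on the treatment indicator" with a random intercept per patient, and uses the same two terms for binary and categorical endpoints. Protocol 10.4 names repeated-measures ANOVA and generalized estimating equations, also without a phase factor. Item 4 tests for a difference by order but does not adjust the treatment estimate for phase.

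Hypotension is recorded at every treatment and troponin T in every phase. Global longitudinal strain (GLS) and ejection fraction (EF) are measured on treatment only in the first phase of each type (4.2.1, 4.2.2, 7.2.2).

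**The concern.** Section 10.5 rests its power claim on each participant serving as his or her own control. Under strict alternation that within-patient contrast is also a contrast in time. Target weight and UF volume stay with the treating nephrologist over the 15 treatment weeks (7.1.1, 7.1.2), so some movement in blood pressure or volume status is plausible, although the documents do not quantify it.

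If a trend common to all patients is left out of the model, two things follow. It goes into the residual and widens the reported interval. And when the two sequences are unequal in number, part of it goes into the treatment estimate. Both can be avoided in the analysis and the randomisation list, without touching the visit schedule.

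**Working it through.** **The plan's own figure.** Section 10.5 gives 5.9 mmHg detectable in nadir systolic BP with N = 30, SD 8 and 80% power. A two-sample t-test with 30 per arm, two-sided 0.05, gives 5.88 mmHg. A paired test with 8 as the SD of differences gives 4.23. No time trend enters either calculation.

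**Time gap.** Write A for conventional and B for UF profiling. Phase starts are 9 + 3 = 12 sessions apart, which is 4 weeks at three per week.
- ABAB: A at phases 1 and 3 (mean 2), B at 2 and 4 (mean 3). B minus A = +1 phase = +4 weeks.
- BABA: −1 phase = −4 weeks.
- GLS and EF, phases 1 and 2 only: also +4 or −4 weeks.

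**Chance shift of the estimate.** With common drift d per phase, the unadjusted estimate moves by d(n₁ − n₂)/30.
- 15:15: 0.
- 18:12: 0.2d, i.e. 0.2, 0.4 or 0.8 mmHg for d = 1, 2 or 4.
- 20:10: d/3, i.e. 0.33, 0.67 or 1.33 mmHg.

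From Binomial(30, 0.5), the probability of 18:12 or worse is 0.362 and of 20:10 or worse 0.099. Over repeated simple randomisation the shift averages zero.

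**Reported standard error at 15:15.** Assumptions: one value per patient per phase (as for troponin T), independent phase-level residual SD 6 mmHg, linear drift d common to all patients. Nadir systolic BP is used because 10.5 gives a scale for it.
- True SD of the estimate: 6/√30 = 1.095.
- The SAP model has 120 − 30 − 1 = 89 residual degrees of freedom. Drift adds d² × [(1.5)² + (0.5)² + (0.5)² + (1.5)²] = 5d² per patient to the residual sum of squares, so 150d² in all.
- Expected residual mean square: 36 + 150d²/89. Reported SE ≈ √[(36 + 150d²/89)/30].

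| d (mmHg per phase) | SE by formula | Simulated mean SE | True SD |
|---|---|---|---|
| 1 | 1.12 | 1.12 | about 1.09 |
| 2 | 1.19 | 1.19 | about 1.09 |
| 4 | 1.45 | 1.44 | about 1.09 |

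At d = 2 under simple randomisation the true SD rises to √[(36 + 4)/30] = 1.155, or about 1.16. With a phase term and 15:15 blocking, the mean SE is 1.09 against a true SD of about 1.10.

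**Per-session data.** If the SD of 6 were purely independent session noise, the session SD would be 6 × √9 = 18. The variance of session times in phase units is 1.25 + (80/12)/144 = 1.296. At d = 2 the residual variance rises from 324 to 324 + 4 × 1.296 = 329.2, so the SE rises by under 1%. The inflation in the table therefore applies to phase-level values. The chance shift is the same in both cases.

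**Why block as well.** With a phase term the variance is (36/4)(1/n₁ + 1/n₂). The SE is 1.095 at 15:15, √1.25 = 1.118 at 18:12 and √1.35 = 1.162 at 20:10.

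**The case against.** Three points can be made for the plan. First, the starting arm is randomised, so a common trend produces no expected bias. That stands. A reader might infer from the four-week gap that the treatment effect is biased, but the documents do not support that: the two sequences carry the gap with opposite sign. What remains is a wider interval and a chance shift in the one trial that is run. Second, the SAP does consider order. It does, but only as a sensitivity test, which leaves the primary estimate and its SE unchanged. Third, no drift is documented, so the effect may be small. That stands too.

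A reader might also infer that alternation is the wrong choice and that ABBA/BAAB must replace it. Those sequences give the same 18 + 18 sessions and a mean gap of zero, so for completers on four-phase endpoints they also remove linear drift that differs between patients, which a phase term cannot do. The advantage depends on the assumptions. With residual SD 6 and simple randomisation, the SE under alternation is larger by √[(36 + m² + s²)/36], where m and s are the mean and between-patient SD of drift per phase:
- m = 2, s = 3: 17%
- m = 1, s = 1.5: 4.4%
- m = 0.5, s = 0.75: 1.1%

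Against this:
- GLS, one of three primary endpoints, and EF gain nothing, since both are measured in phases 1 and 2.
- If adjacent phases are positively correlated (AR(1), ρ = 0.1, 0.3, 0.5), the SE under ABBA is 5%, 11% and 13% larger. The variances are proportional to 4 − 2ρ − 4ρ² + 2ρ³ for ABBA and 4 − 6ρ + 4ρ² − 2ρ³ for ABAB.
- A patient who leaves after phase 3 has a gap of zero under ABAB but 1.5 phases (6 weeks) under ABBA.
- A single step change, such as a revised target weight, gives the same absolute error in both.

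**Conclusion.** The point holds as a gap in the SAP models and the randomisation list, not as a fault in the choice of sequences. Every completer's contrast spans four weeks, and nothing in the planned analysis removes a common trend. For phase-level values, under the assumptions stated, the reported SE at 15:15 is about 2%, 9% or 32% too large (1.12, 1.19 or 1.44 against about 1.09) for drift of 1, 2 or 4 mmHg per phase. At an 18:12 split the estimate shifts by 0.2 to 0.8 mmHg over the same range, against the 5.9 mmHg target. These drift values and the residual SD of 6 are assumptions. With little drift, or for endpoints analysed session by session with mostly independent noise, the effect on the SE is small. ABBA/BAAB is an option to weigh, not a required change.

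**What to change.** In the SAP, add phase (1 to 4) as a categorical fixed effect to every primary model: linear, logistic and multinomial. For GLS and EF this becomes phase 1 versus 2. Align Protocol 10.4 with the same term, and keep sensitivity analysis 4 as a separate check. In Protocol 10.6.1, state 1:1 allocation to the two sequences in permuted blocks, preferably of varying size, so that the counts stay close to equal through replacement of withdrawals.

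The cost is a sentence in each section, a new randomisation list before first enrolment, and up to 3 degrees of freedom (1 for GLS and EF). Sessions, visits and echocardiograms are unchanged. With no drift and balanced sequences, the loss of precision is negligible. The phase term does not remove drift that differs between patients. If the investigators expect that to be large and roughly linear, they can consider ABBA/BAAB with the drawbacks above in view.
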